2.11 Patient-reported outcomes

Not applicable

2.13 Interim analysis

No formal interim analyses are planned. However, the dose-escalation design foresees that decisions based on the current data are made before the end of the study. More precisely, the next dose of LDK378 has to be chosen after each cohort in the dose escalation part, and the decision is dependent on the observed data.

3 Sample size calculation

Dose escalation part

Respectively for the fasted dose escalation and the fed dose escalation, cohorts of 3 to 6 evaluable patients will be dosed in the dose-escalation part including at least 6 patients at the corresponding MTD/RDE level, as described in Section 6.2.3 of protocol. Multiple cohorts may be sequentially enrolled to the same dose level. Additional cohorts of 1 to 6 patients may be enrolled at any dose level below the estimated MTD/RDE for further elaboration of safety and pharmacokinetic parameters as required. At least 15 patients for the fasted dose escalation and 12 for the fed dose escalation are expected to be treated in the dose escalation part, for the model to have reasonable operating characteristics relating to its MTD recommendation.

Dose expansion part

During the expansion part, approximately 45 patients will be treated on the preferred regimen (including all patients treated at the MTD/RDE on the preferred regimen during the dose escalation part who are eligible for the safety set), approximately 25 patients in group 1 on the preferred regimen, and approximately 20 patients in group 2.

Group 1: ALK-activated neuroblastoma

Based on the ORR (per RECIST 1.1) intervals described in Section 10.4.2 of protocol, it was assessed how likely it is to wrongly declare activity as defined by observing at least “moderate antitumor activity” (i.e. seeing at least 5 responses out of 25 patients) given the true ORR = 10%, and how likely it is to correctly declare activity given the true ORR = 30% when 25 patients are evaluated.

- If the true ORR = 10%, the probability to wrongly declare activity is 9.8%.
- If the true ORR = 30%, the probability to correctly declare activity is 91.0%.

Given a sample size of 25 in-group 1, if five responses are seen, the observed ORR is 20% with an 80% credible interval of (10.7%, 30.3%). This will be considered as preliminary evidence of antitumor activity of LDK378 at the MTD/RDE within this group.

Group 2: other ALK-activated tumors, such as IMT and ALCL

For group 2, sample size estimation is based on safety. A sample size of 20 will result in an 87.8% probability of detecting an AE with an incidence rate of $\geq 10\%$.

4 Change to protocol specified analyses

[Table 4-1](#) summarizes the changes to protocol-specified analyses and associated rationale for inclusion.

Table 4-1 Changes to protocol specified analysis or descriptions and rationale

Protocol Section	Protocol Description	Change
3.1 Best overall response	
BOR for each patient will be determined based on the following rule:
 
 • SD = at least one SD assessment (or better) > 6 weeks after randomization (and not qualifying for CR or PR). • PD = progression ≤ 12 weeks after randomization (and not qualifying for CR, PR or SD). 	
BOR for each patient will be determined based on the following rule:
 
 • SD = at least one SD assessment (or better) > 29 days after randomization (and not qualifying for CR or PR). • PD = progression ≤ 85 days after randomization (and not qualifying for CR, PR or SD). 
This update was made to account for the +/-1 week window for the tumor assessment protocol defined schedule of 6 weeks. Consequently, BOR of 'Unknown' derivations of 'SD too early' and 'PD too late' will be based on the updated calculations:
 
 • Stable disease (SD) too early (≤ 29 days after randomization date) • PD too late (> 85 days after randomization date). 
See details in section 2.6.

3.1 Best overall response	
As a default, any assessments taken more than 30 days after the last dose of study treatment will not be included in the best overall response derivation.
	
For the BOR calculation, the default option will not be used, i.e., assessments taken more than the 30 days after the last dose of study treatment will be included in the best overall response derivation for consistency with other time to event end-points.

5 Appendix

The sections below contain additional details on statistical methodology that will be included in Appendix 16.1.9 (Documentation of Statistical Methods) of the CSR as well as rules details on programming rules that will be followed to implement the analyses described in [Section 2](#).

5.1 Data included in the analyses

This section provides additional details to those included in [Section 2.1](#).

Final analysis of study data once all patients have discontinued treatment, and all required safety follow-up has been completed or the patient has died, been lost to follow-up or has withdrawn their consent to further participation in the study or the last patient on treatment has been enrolled to a separate protocol, whichever comes first, will include the data with an assessment date or event start date (e.g. vital sign assessment date or start date of an adverse event) prior to or on the cut-off date. For example, if the cut-off date is 30DEC2015, an AE starting on 28DEC2015 will be reported, whereas an adverse event starting on 31DEC2015 will not be reported.

5.2 Patient classification into analysis sets

This section provides additional details to those included in [Section 2.2](#).

Patients are excluded from the analysis populations based on the protocol deviations entered in the database and/or on specific patient classification rules as shown in [Table 5-1](#) below. Only data from patients having signed informed consent are used in the analyses described below.

Table 5-1 Patient classification rules

Analysis Population	Protocol deviation ids leading to exclusion	Additional patient classification rules leading to exclusion
Full Analysis Set	N/A	Patients who did not receive at least one dose of study drug
Safety Set	N/A	Patients who did not receive at least one dose of study drug.
Dose determining Set	N/A	Patient did not received at least 16 of the 21 doses in cycle 1 or did not experience a DLT if receiving less than the prescribed number of doses.
Pharmacokinetic analysis set	N/A	Patients receiving LDK who do not have at least one evaluable PK sample as defined in Section 2.10

5.3 Derivations

Month derivation

For all derivations, a month will be calculated as $(365.25 / 12) = 30.4375$ days. If duration is to be reported in months, duration in days will be divided by 30.4375.

Dose interruptions and dose changes

This section provides additional details to those included in [Section 2.4](#).

All calculations of dose interruptions and dose changes are based on corresponding CRF check box and the dose actually taken by the patient.

An interruption is defined as a 0 mg dose taken on one or more days. What follows defines how dose interruptions will be counted in the case of multiple dose interruptions.

- If an interruption occurs consecutively for at least two days due to the same reason, then it will be counted only once (*example: If the actual dose on days 1-3 is 750 mg and actual dose on days 4-5 is 0 mg and dose interruption on days 4-5 is due to AE, then the total number of dose interruptions is 1*).
- If an interruption occurs consecutively for at least two days due to different reasons, then it will be counted for each reason (*example: If the actual dose on days 1-3 is 750 mg and actual dose on days 4-5 is 0 mg and dose interruption on day 4 is due to AE and dose interruption on day 5 is due to dosing error, then the total number of dose interruptions is 2*).
- If an interruption occurs for more than one day due to the same reason, but the days are not consecutive, i.e. there is at least one dosing day in between, then each dose interruption will be counted as a different occurrence (*example: if the actual dose on days 1, 3 and 5, is 750 mg and actual dose on days 2 and 4 is 0mg, and dose interruptions on day 2 and 4 are both due to dosing error, the total number of dose interruptions is 2*).

A dose change is defined as a change in dosing from one record to the next; however, a dose interruption will not be counted as a dose change.

Dose reductions are a subset of dose changes where dose changes to higher than protocol-planned dose are excluded.

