#### 6.1.1 Dosing regimen

LDK378 dose will be scaled by BSA. The dose will be adjusted to the nearest 50 mg, and the minimum dose will be 50 mg. LDK378 will be administered once daily by mouth, or by NG tube or G tube. For patients who are not able to swallow the capsules, or who will receive LDK378 through a NG tube or G tube, the capsules will be opened, and the contents mixed with an appropriate food or liquid. Further detailed instructions regarding capsule opening and administration will be provided to all study sites separate from this protocol.

The study site staff will inform each patient of their actual daily dose, and this will be recorded on the appropriate eCRF. The actual dose for each patient will be calculated using a body surface area (BSA) conversion as follows:

- Actual dose in mg = (planned dose level (mg/m^2) x BSA) rounded to the nearest 50 mg

Individual patient BSA will be calculated using their height and weight as per standard site procedure. The actual dose for Cycle 1 will be based on the BSA calculation at screening. Dosage adjustments for changes in BSA in subsequent cycles will be made as per standard site practice (e.g., if the BSA changes by  $\pm$  10% from the previous dose calculation).

[figure not shown]
Individual doses will consist of the minimum number of capsules possible given based on the available capsule sizes, and will be rounded to the nearest 50 mg.

The investigator should instruct the patient to take the LDK378 exactly as prescribed below. All dosages prescribed and dispensed to the patient, and all dose changes during the study must be recorded on the appropriate eCRF. Patients/guardians will be asked to complete a paper dosing diary starting Cycle 1 Day 1 and will return the paper dosing diary to the study site at the beginning of each subsequent cycle (cycle 2 and on). A new diary will be dispensed to the patient at the beginning of each new cycle.

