#### 10.7.1.5 Supportive analyses for secondary objectives

##### 10.7.1.6 Tolerability

Tolerability of LDK378 will be assessed by summarizing the number of dose interruptions and dose reductions. Reasons for dose interruption and dose reductions will be listed by patient and summarized. Cumulative dose, dose intensity and relative dose intensity of LDK378 will be listed by patient and summarized. Categories for relative dose intensity of LDK378 will be specified as  $< 0.5$ ,  $\geq 0.5 - < 0.75$ ,  $\geq 0.75 - < 0.9$ ,  $\geq 0.9 - < 1.1$  and  $\geq 1.1$ . The number and proportion of patients within each category will be presented.

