2.2 Analysis sets

A patient is considered to be enrolled into the study if they have signed study informed consent. Only patients who have signed study informed consent prior to study procedures will be included in the analysis data sets.

Full analysis set

The Full Analysis Set (FAS) includes all patients who received at least one dose of LDK378. Patients will be classified according to the intended/planned treatment. The FAS will be used for all listings of raw data. Unless otherwise specified, the FAS will be the default analysis set used for all analyses.

The planned treatment will be based on the first dosing record. The corresponding fasted/fed status will be determined as per [Table 2-1](#) below as per protocol.

Table 2-1 Dose level and fasted/fed status

Dose Levels	Fasted/Fed Status
200 mg/m ²	Fasted
300 mg/m ²	Fasted
450 mg/m ²	Fasted
510 mg/m ²	Fasted
560 mg/m ²	Fasted
320 mg/m ²	Fed
400 mg/m ²	Fed
500 mg/m ²	Fed

Safety set

The safety set includes all patients who received at least one dose of LDK378.

The patients will be classified according to treatment received, where treatment received is defined as:

1. The actual dose level (mg/m^2) is the planned dose level if any actual total daily dose administered is equal to the value of “the planned dose levels ([Table 2-1](#)) * BSA (m^2) rounds to the nearest 50 mg”. For 25/75 mg, either rounding up or rounding down is acceptable.
2. The first actual dose level in the study (converts actual total daily dose administered / BSA (m^2) and maps to nearest planned dose levels) if the planned dose level was never received.

BSA = The last available BSA measurement on or before dosing date will be used in the calculation for actual dose level.

For example, if a patient from 500 mg/m^2 fed group doesn't meet the first criteria, and the first actual dose level in the study is 150 mg. Suppose this patient has BSA=0.45 m^2 on/before the first dose, then the first actual dose level in the study=actual total daily dose administered / BSA (m^2)=333 mg/m^2 , which will be rounded to the nearest planned dose level 320 mg/m^2 fed.

Dose determining set

The dose determining analysis set (DDS) consists of all patients from the safety set who *either* meet the minimum exposure criterion and have sufficient safety evaluations *or* discontinue earlier due to DLT in the escalation phase.

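### The SAP's definition of a dose reduction does not require the dose to fall, so increases made only because BSA rose can be counted as reductions

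*SAP*

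**What the plan says.** SAP 5.3 builds the definition in two steps. First: "A dose change is defined as a change in dosing from one record to the next", with the proviso that "a dose interruption will not be counted as a dose change". Then: "Dose reductions are a subset of dose changes where dose changes to higher than protocol-planned dose are excluded". The source is given as: "All calculations of dose interruptions and dose changes are based on corresponding CRF check box and the dose actually taken by the patient". The section does not say what the planned dose is, or how a resumption after a 0 mg record is treated.

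Protocol 6.1.1 sets the milligram dose as the planned level times BSA, rounded to the nearest 50 mg, and adds: "Dosage adjustments for changes in BSA in subsequent cycles will be made as per standard site practice". A BSA change of 10% is offered there as an example of a trigger. Protocol 7.2.2.3 has BSA measured on Day 1 of every cycle from Cycle 2. When SAP 2.2 checks a dose against a planned level for the safety set, it specifies: "The last available BSA measurement on or before dosing date will be used in the calculation for actual dose level".

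On reporting, Protocol 10.7.1.6 says: "Tolerability of LDK378 will be assessed by summarizing the number of dose interruptions and dose reductions". SAP 2.4.1 tabulates the number and percentage of patients with reductions or interruptions, with reasons. It specifies a per-patient number only for interruptions.

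**The concern.** A reduction should mean that the dose went down. The SAP instead takes every change in either direction and removes only those that end above the planned dose. An upward change ending at or below the planned dose stays in and becomes a reduction.

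This would do little harm with a flat dose, and the worked examples in SAP 5.3 do use a flat 750 mg. Here the patients are children dosed by BSA, and the protocol anticipates upward adjustments that have nothing to do with tolerability. Two outputs are at stake: the number of reductions (Protocol 10.7.1.6) and the number of patients with a reduction (SAP 2.4.1). A child who grew and never had the dose reduced could enter the second.

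**Working it through.** The plan states no count of dose reductions, so there is no figure to reproduce. The check applies the SAP rule literally to short dose histories and compares it with the actual number of decreases.

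**Inputs.** Dose = level × BSA, rounded to 50 mg (Protocol 6.1.1). Levels of 500 mg/m² and, after one reduction step, 400 mg/m² (Protocol Table 6-3). The BSA values and dose histories are my assumptions, not trial data.

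**SAP rule, literally.** Count a record if its dose is non-zero, differs from the previous non-zero dose, and is not above the planned dose. Because the planned dose is undefined, I use two readings: (A) it follows current BSA; (B) it is fixed at the starting milligram dose.

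**Doses.**
- 500 × 0.60 = 300 mg; 500 × 0.70 = 350 mg; 500 × 0.80 = 400 mg.
- 400 × 0.60 = 240, rounded to 250 mg; 400 × 0.70 = 280, rounded to 300 mg; 400 × 0.80 = 320, rounded to 300 mg.

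| Assumed history | Doses (mg) | Reading A | Reading B | Actual decreases |
|---|---|---|---|---|
| 1. Growth only at 500 mg/m², BSA 0.60, 0.70, 0.80 | 300, 350, 400 | 2 | 0 | 0 |
| 2. Reduced to 400 mg/m² at BSA 0.60, then growth to 0.70 and 0.80 | 300, 250, 300, 300 | 2 | 2 | 1 |
| 3. One lower dose, then back to planned | 500, 400, 500 | 2 | 2 | 1 |
| 4. Interruption, same dose resumed | 500, 0, 500 | 0* | 0* | 0 |

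*1 if the step from 0 mg back to 500 mg is itself treated as a change.

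**Which output each history affects.** History 1 under reading A puts a patient with no reduction into the SAP 2.4.1 patient count. In histories 2 and 3 the patient already has a genuine decrease, so only the number of reductions in Protocol 10.7.1.6 is inflated.

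**Are the BSA steps enough to trigger a new dose?** 0.10/0.60 = 16.7% and 0.10/0.70 = 14.3%, both above the protocol's example of 10%. The same 0.10 m² at 1.5 m² is 6.7% and would not trigger a change under that example. The problem therefore bears mainly on smaller children.

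**Does reading B repair the rule?** No. History 2 still gives 2 against 1, and reading B can also lose a true reduction. Take BSA 0.54 m² at the start: 500 × 0.54 = 270, rounded to 250 mg. Growth to 0.69 m² gives 345, rounded to 350 mg. A reduction to 400 mg/m² gives 276, rounded to 300 mg. The dose has fallen from 350 to 300 mg, but 300 exceeds the starting 250 mg, so the rule excludes it.

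**Comparing mg/m² levels instead.** History 1: 300/0.60 = 350/0.70 = 400/0.80 = 500 mg/m², so 0 reductions. History 2: 300/0.60 = 500; 250/0.60 = 417, nearest level 400, so one reduction; then 300/0.70 = 429, still nearest to 400, so no further one. History 3 gives 1 and history 4 gives 0. All four match the actual decreases.

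**The case against.** The strongest reply is that the derivation also rests on a CRF check box whose content the documents do not show. It may already separate reductions from BSA adjustments. SAP 2.4.1 also requires reasons and a listing of all doses with change reasons, so a BSA-driven entry could be visible. This stands as a limit on the likely size of the error. It does not change the written definition.

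Second, the planned dose could mean the fixed starting milligram dose, and the latest-BSA rule in SAP 2.2 belongs to the safety-set classification. On that reading, growth at full dose is not counted. This is fair, but SAP 5.3 does not say so, the only planned-dose formula in the documents is level times BSA, and the fixed reading fails in other ways, as shown above.

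Third, reductions are one tolerability measure among several. Protocol 10.7.1.6 also uses interruptions, cumulative dose and dose intensity, and Protocol 7.2.2 refers to adverse events leading to delay or discontinuation. This stands.

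A reader might infer more than the documents support:
- **That returns to the planned dose inflate the patient count.** They do not: such a patient already has a genuine decrease. Protocol 6.3.1 bars re-escalation after a reduction, so returns should come mainly from dosing errors or deviations. SAP 2.1 also drops data after a first intra-patient escalation from the summaries.
- **That resuming the same dose after an interruption is a reduction.** The SAP is silent on resumption, but this reading is strained given that interruptions are not dose changes.
- **That long-treated responders will look least tolerant.** Growth does accumulate with time, but no analysis of reductions by response is planned and no data here show such a pattern.

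**Conclusion.** The definition is wrong as written, not merely short of detail: programmed literally, it can label an increase as a reduction. Increases due only to a rise in BSA are caught at full dose if the planned dose follows current BSA. After a true reduction they can be caught under either reading. The number of reductions, and under the first reading the number of patients with one, can therefore be overcounted.

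The amount cannot be computed. It depends on how often doses were recalculated, on the meaning given to the planned dose, and on the check box. That overcounting will occur is not established; that the rule permits it is. The consequence is confined to a descriptive secondary tolerability summary. DLT and MTD estimation and relative dose intensity do not use this definition.

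**What to change.** Replace the sentence in SAP 5.3 with a directional definition, to this effect: a dose reduction is a dose change to a lower dose level, in mg/m² using the BSA in force for each dose, than that of the last non-zero dose. Then add:

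- Changes due only to BSA recalculation or rounding, in either direction, are classified and reported separately.
- The dose on resumption after an interruption is compared with the last non-zero dose.
- If the term planned dose is kept anywhere in the section, it is defined.
- The SAP states whether correcting an overdosing error counts. A purely directional rule counts 500, 600, 500 mg as one reduction.

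This concerns only how changes are counted for analysis; it alters no dosing instruction. The cost is a few sentences in SAP 5.3 and a small programming change made before database lock. Doses, BSA and change reasons are already collected.

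If the check box already distinguishes these categories, saying so in SAP 5.3 would cover part of the point, but the definition should still require a decrease.

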5.4 Efficacy endpoints

For further details on efficacy endpoints, see Section 14 (Appendix 5 and 6) of the protocol. For the evaluation of tumor-response related endpoints, response is assessed by investigator per RECIST 1.1 and IWG criteria.

Response and progression evaluation will be performed according to the Novartis RECIST 1.1 guidelines and the Novartis Cheson criteria guidelines, included in Section 14 (Appendix 5 and 6) of the LDK378X2103 protocol.

The text below gives more detailed instructions and rules needed for programming of the analyses described in Sections [2.6](#) and [2.7](#)

5.4.1 Implementation of RECIST and Cheson guidelines

Disease progression

PD should only be assigned if it is confirmed by an objective assessment method. If a new lesion is detected using an objective assessment method other than radiologic scan, it should be entered on the 'New lesion' RECIST and Cheson eCRF with appropriate method (or method='Other').

In particular, discontinuation due to disease progression or death due to progressive disease, without supporting objective evidence (as defined above), will not be considered as PD in the determination of BOR, the derivation of any efficacy endpoint or efficacy analysis.

Change in imaging modality per RECIST 1.1

Per RECIST 1.1, a change in methodology can be defined as either a change in contrast use (e.g. keeping the same technique, like CT, but switching from with to without contrast use or vice-versa, regardless of the justification for the change) or a change in technique (e.g. from CT to MRI, or vice-versa), or a change in any other imaging modality. A change in methodology will result by default in a UNK overall lesion response assessment. However, another response assessment than the Novartis calculated UNK response may be accepted from the investigator or the central blinded reviewer if a definitive response assessment can be justified, based on the available information.

Change in imaging modality per Cheson

A change in methodology can be defined as either a change in contrast use (e.g. keeping the same technique, like CT, but switching from with to without contrast use or vice-versa, regardless of the justification for the change) or a change in technique (e.g. from CT to MRI, or vice-versa), or a change in any other imaging modality. A change in methodology will result by default in an "Unknown" overall radiological response assessment. However, another overall radiological response than the Novartis calculated "Unknown" response might be accepted from the investigator or the central blinded reviewer if a definitive overall radiological response can be justified to be based on the available information.

Determination of missing adequate tumor assessments

For the computation of ORR, patients without any radiological assessment after the start date of study drug will be counted as failure.

Partial or complete responses reported prior to any additional anticancer therapy will be considered for ORR computation irrespective of the number of missed assessments before response. In this section, the 'missing adequate assessment' is defined as assessment not done or assessment with overall lesion response equal to UNK. For the sake of simplicity, the 'missing adequate assessment' will also be referred as 'missing assessment'.

As detailed in Section 14 (Appendix 5 and 6) of the LDK378X2103 protocol, the PFS censoring and event date options depend on the presence and the number of missing tumor assessments. *For example, an event occurring after two or more missing assessments is censored in the analysis of PFS at the last adequate tumor assessment before the event date.*

An exact rule to determine whether there is none, one or two missing assessments is therefore needed. This rule will be based on the distance between the last adequate tumor assessment date and the event date.

If the distance is larger than threshold D_1 or D_2 then the analysis will assume one or two missing assessments, respectively. The threshold D_1 will be defined as the protocol specified interval between the tumor assessments plus the protocol allowed window around the assessments. Similarly, the threshold D_2 is defined as two times the protocol specified interval between the tumor assessments plus the protocol allowed window around the assessments. For example, in this study, the protocol defined schedule of tumor assessment is every 6 weeks for the first six cycles, and each assessment is expected to be performed at the scheduled time point plus or minus 1 week, i.e. the window is 2 weeks, then any distance larger than $D_1 = 6+2 = 8$ weeks means one missing assessment and any distance larger than $D_2 = (2*6) + 2 = 14$ weeks means two missing assessments. Please see protocol 7.1 for the complete schedules for tumor assessments.

The same definition of D_2 will be used to determine the PFS censoring reason. Possible censoring reasons for PFS are:

- 1: Ongoing without event
- 2: Lost to follow-up
- 3: Withdrew consent
- 4: Adequate assessment no longer available
- 5: New cancer therapy added
- 6: Event after ≥ 2 missing tumor assessments

New cancer therapy used in RECIST calculations include any anti-cancer therapy as recorded in the medication, surgery (diagnostic biopsies are excluded) or radiotherapy CRF pages and includes LDK378 treatment from the extension-treatment phase.

Eligibility per RECIST 1.1 (Non-measurable disease only at baseline)

As specified in Section 14 (Appendix 5) of the LDK378X2103 protocol, the RECIST 1.1 criteria imply that only patients with measurable disease at baseline should be included in the study.

If a patient without measurable disease is enrolled, the intent-to-treat (ITT) principle requires including these patients in the analyses. Hence, analyses will be based on FAS including patients with either measurable or non-measurable disease per RECIST 1.1. Therefore, a rule needs to be specified on how to handle these cases.

As specified in Table 14-8 of Section 14 (Appendix 5) of the LDK378X2103 protocol, overall lesion response can be derived for patients without measurable disease at baseline as follows ([Table 5-2](#)).

Table 5-2 Overall lesion response at each assessment: patients with non-target disease only

Non-target lesions	New Lesions	Overall lesion response
CR	No	CR
Non-CR/Non-PD ¹	No	Non-CR/non-PD
UNK	No	UNK
PD	Yes or No	PD
Any	Yes	PD

¹ In general, the **non-CR/non-PD response** for these patients is considered equivalent to an SD response in endpoint determination.

Eligibility per Cheson criteria.

As specified in Section 14 (Appendix 6) of the LDK378X2103 protocol, Cheson criteria imply that only patients with measurable disease should be included in the study. In particular, patients should have **at least one measurable nodal lesions greater than 20mm in the long axis**. In cases where the patient has no measurable nodal lesions greater than 20mm in the long axis at baseline, then the patient must have at least one measurable extranodal lesion (long and short axes are ≥ 10 mm).

Missing baseline tumor assessment

Since the timing of PD cannot be determined for patients with missing baseline tumor assessment, these patients are censored in the PFS analysis at the start date of treatment. This rule, however, only applies to the 'PD component' of the PFS or DOR assessment.

Patients without baseline tumor assessment who die within D₂ distance from start date of treatment will be counted as having an event in the primary analysis of PFS.

